4. INVESTIGATIONAL PLAN

4.1. Overall Study Design and Plan

This is a phase 3, parallel group, double blind, vehicle-controlled study in which ARQ-154 foam 0.3% or vehicle foam is applied QD x 8 weeks to adolescent and adult subjects with a minimum Scalp Investigator Global Assessment (S-IGA) of 'Moderate' (3) and a minimum rest of the Body Investigator Global Assessment (B-IGA) of 'Mild' (2).

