4.8.3. Treatment Compliance

Weight of the IP applied will be measured for reporting purposes. Each IP canister will be weighed individually prior to dispensing at the Baseline visit or subsequent visits. IP canisters must be returned by subjects at each study visit (both empty and full) and will be weighed individually. Record IP canister weight in the source notes and in the eCRF.

Subjects will complete a daily diary recording the date and time of each dose applied, any missed doses, and a comment section should the subjects have a comment, e.g., record potential AEs or reason for missed dose. Site personnel will review the diaries and use the information to question the subject regarding compliance and AEs and then record appropriate information in source documents and complete eCRFs. If a subject misses a scheduled dose, they should be

instructed to return to the protocol IP administration schedule (i.e., if subject forgets a dose they should wait until that evening and apply as usual).

A subject will be considered compliant with the dosing regimen if the subject applies at least 80% of the expected applications during the entire IP application period (Baseline to Week 8) and does not miss more than 3 consecutive doses.

Compliance will be assessed by review of the dosing diary. Re-training will be conducted at subsequent visits as needed, i.e., if the returned canister weighs substantially different than the expected weight, the diary shows less than 80% of expected use, or more than 3 consecutive doses are missed.

Compliance will be documented in the source and eCRF.

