3.7. Schedule of Events

A detailed schedule of events for the study is provided in [Table 1](#).

Table 1: Schedule of Events

| Study Procedure | Screening | Baseline Day 1 | Week 2 Day 15 | Week 4 Day 29 | Week 8 ^a Day 57 |
|--|-----------|-------------------|-----------------------|------------------|-------------------------------|
| Visit | 1 | 2 | 3 | 4 | 5 |
| Visit Window | -4 Weeks | | ± 3 Days | ± 5 Days | ± 5 Days |
| Informed consent/assent | X | | | | |
| Medical/surgical history, demography | X | | | | |
| Physical examination ^b | X | X | | | X |
| Fitzpatrick Skin Type | X | | | | |
| I/E criteria | X | X | | | |
| Randomization | | X | | | |
| Hematology, Chemistry, and Urinalysis ^c | X | X | | X | X |
| Vital signs, weight, height ^d | X | X | X | X | X |
| S-IGA ^e , B-IGA ^e , PSSI ^e , BSA ^f , Extent of Scalp Involvement ^g , PASI | X | X | X | X | X |
| DLQI/CDLQI ^h , Scalpdex ^h , PSD ^h | X | X | X | X | X |
| Daily SI-NRS and WI-NRS ⁱ at home (non-clinic) | | | Day -7 through Day 57 | | |
| Application Site Reaction Assessment/ Local Tolerability ^j | | X | X | X | X |
| C-SSRS, PHQ-8/PHQ-A ^k | X | X | | X | X |
| Medical Photography ^l | | X | X | X | X |
| Follicle Stimulating Hormone (FSH) ^m | X | | | | |
| Serum pregnancy test ^m | X | | | | |
| Urine pregnancy test ⁿ | | X | | X | X |
| PK sampling ^o | | | | X | X |
| IP application and subject/family training ^p | | X | X | X | |
| Dispense investigational product kit ^q | | X | X | X | |
| Dispense / review dosing diary | | X | X | X | X |
| Weigh investigational product ^r | | X | X | X | X |
| Compliance calculation ^s | | | X | X | X |
| Adverse event assessment ^t | X | X | X | X | X |
| Concomitant medications | X | X | X | X | X |

Footnotes from table above:

- a. Subjects that terminate early should return to the study site for the Week 8 assessments.
- b. Limited physical examination: skin (including assessment of Fitzpatrick Skin Type at Screening only), lungs, and heart only.
- c. For subjects <18 years of age, if the Baseline/Day 1 visit occurs within 3 weeks of Screening, the Screening lab results may be utilized.

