5. ANALYSIS POPULATIONS

The following analysis populations are planned for this study:

- **Safety Population (SAF):** The Safety population will include all subjects who are randomized and received at least 1 confirmed dose of investigational product (IP). This population will be used for all safety analyses.
- **Intent-To-Treat Population (ITT):** The ITT population will include all randomized subjects. This population will be the primary analysis population for the analysis of efficacy endpoints, along with subject disposition.

- **Per Protocol (PP) Population:** The PP population will include the subjects in the ITT population who were at least 80% compliant with study drug application, have an S-IGA and B-IGA assessment at Week 8, and showed no important deviations from the study protocol that would affect the interpretation of efficacy. “Important deviations” will result from a blinded review at the end of the study and the team will determine the important deviations that can impact on efficacy. This population will be used for a supplemental analysis for primary efficacy endpoints.
- **Modified Intent-to-Treat Population (mITT):** The mITT population includes all randomized subjects with the exception of subjects who missed the Week 8 S-IGA or B-IGA assessment specifically due to COVID-19 disruption. This population will be used for sensitivity of the primary endpoints.
- **Scalp Pruritus ITT Population (SPRU4-ITT):** The SPRU4-ITT population is a subset of the ITT population and includes subjects with average weekly SI-NRS score ≥ 4 at baseline. This population will be used for the analysis of achievement of at least 4-point reduction in average weekly SI-NRS score as compared to baseline.
- **Pruritus ITT Population (PRU4-ITT):** The PRU4-ITT population is a subset of the ITT population and includes subjects with average weekly WI-NRS score ≥ 4 at baseline. This population will be used for the analysis of achievement of at least 4-point reduction in average weekly WI-NRS score as compared to baseline.
- **Pharmacokinetic Population (PK):** The PK population will include all subjects who received at least one confirmed dose of investigational product (IP) and provided at least one PK sample. This population will be used for summary of PK concentration results for subjects who applied roflumilast foam 0.3% during this study.

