- **CDLQI Score** (Children's Dermatology Life Quality Index for ages 12-16 years) = sum of the 10 questions (individual questions scored as Very much=3, Quite a lot=2, Only a little=1, Not at all=0; Question 7: if the last week was school time, the question was scored as Very much=3, Quite a lot=2, Only a little=1, Not at all=0, with Prevented school recoded to 3, and if the last week was vacation, the standard responses apply; range for score 0 to 30). If 1 item is missing, that item is scored as 0. If 2 or more items are missing, the score should not be calculated.
- **Compliance** = number of applications divided by the expected number of IP applications for each subject. Compliance will be calculated using drug accountability data over the entire treatment period for each subject, up to treatment completion or discontinuation.
 - **Number of Expected IP Applications** = calculated as last treatment/interruption date – first treatment date + 1. If last treatment date \geq last interruption date, then the last treatment date will be used; otherwise, last interruption date will be used in deriving the expected number of IP applications.
 - **Number of IP Applications** = number of expected IP applications – missed IP applications as collected in the eCRF.
 - **Number of Days on IP** = last treatment date – first treatment date + 1.
- **Body Mass Index (BMI) (kg/m²)** = (weight in kg)/[(height in cm/100)²]. For Week 8, Week 8 height will be used to derive BMI since height is not collected at all visits.
- **BMI Categories**
 - Underweight: BMI < 18.5
 - Normal: 18.5 \leq BMI \leq 24.9
 - Overweight: 25.0 \leq BMI \leq 29.9
 - Obese: BMI \geq 30.0
- **Age Categories:**
 - 12 – 17 years
 - 18 – 64 years
 - \geq 65 years
- **Change from Baseline** = value at current time point – value at baseline.
- **Duration (months) since onset of scalp and/or body psoriasis is derived as:**
 - (Randomization date – onset date)/30.4375
 - If day of onset is not available, assume that onset occurred on the 1st of the month.
- **Treatment-emergent AE (TEAE)** = any AE with an onset date/time after the first application of IP.

- **PHQ-8** = sum of the 8 questions (individual questions scored as Not at all=0, Several days=1, More than half the days=2, and Nearly every day=3; range for score 0 to 24). If more than 1 item is missing, the score should not be calculated. If 1 item is missing, the score is calculated as (sum of answered items*8)/number of answered items.

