7.4. Exposure and Compliance

The number of expected IP applications will be summarized by treatment group.

The number of IP applications by each subject based on diary data will be summarized using descriptive statistics appropriate for continuous variables.

The amount of IP each subject used based on can weight will be summarized descriptively by treatment group using continuous methods.

The number of days on IP will be summarized descriptively by treatment group.

A subject will be considered compliant with the dosing regimen if the subject applies at least 80% of the expected applications during the treatment period and does not miss more than 3 consecutive doses.

Investigational product application compliance will be calculated based on number of applications divided by the expected number of IP applications. Compliance will be summarized descriptively by treatment group using the following categories:

- $> 100\%$
- $\geq 80\% - \leq 100\%$
- $< 80\%$

A listing of drug exposure, compliance and accountability will also be provided.

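### SAP compliance runs only to the subject's own last dose or interruption, not to Week 8 as in the protocol, so an adherent early stopper passes the 80% threshold and may enter the Per Protocol set

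*SAP*

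**What the plan says.** Protocol 4.8.3 calls a subject compliant who "applies at least 80% of the expected applications during the entire IP application period (Baseline to Week 8") and who misses no more than 3 doses in a row.

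SAP 6.1.7 sets a different period: "Compliance will be calculated using drug accountability data over the entire treatment period for each subject, up to treatment completion or discontinuation". The denominator, expected applications, is "calculated as last treatment/interruption date – first treatment date + 1", where the later of the last treatment and last interruption dates is used. The numerator is "number of expected IP applications – missed IP applications as collected in the eCRF".

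SAP 7.4 restates the protocol rule without its Baseline-to-Week-8 wording: a compliant subject "applies at least 80% of the expected applications during the treatment period and does not miss more than 3 consecutive doses". It then tabulates compliance in three bands, one of them above 100%.

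The PP set in SAP section 5 takes ITT subjects "who were at least 80% compliant with study drug application, have an S-IGA and B-IGA assessment at Week 8", and also requires that a blinded review find no important deviation bearing on efficacy. It gives no minimum time on treatment and does not mention the limit on consecutive missed doses. SAP 8.1.4 uses this set, with observed data, for a supplemental analysis of both co-primary endpoints.

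SAP section 11, which records departures from the protocol such as the PK population definition, is silent on the compliance denominator.

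**The concern.** A denominator that normally closes with the subject's own dosing measures adherence while on treatment. It does not measure how much of the planned course was used, which is what the protocol's definition asks. A subject who applies every dose for two weeks and then stops looks fully compliant.

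Two outputs depend on this. The compliance table can show early stoppers as adherent, more so in an arm with more early stopping. The PP analysis, which a reader takes as the effect in subjects who used the product as planned, can include subjects with a small part of the planned exposure.

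**Working it through.** The documents print no compliance figure, expected count or PP size, so there is no stated result to reproduce. The check compares the two written definitions.

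**Inputs**
- Planned dosing: product "is applied QD x 8 weeks to adolescent and adult subjects" (protocol 4.1). Once daily for 8 weeks is 7 × 8 = 56 applications, Day 1 to Day 56. The count of 56 is derived. The Week 8 visit is Day 57 ± 5 days, so the day before it ranges from Day 51 to Day 61.
- SAP ratio = (expected − missed) / expected, where expected = stop day if no later interruption date is recorded.
- Protocol ratio = applications / 56.

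**Results by day of last dose**

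| Last dose | SAP, none missed | SAP, 2 missed | Protocol, none missed |
|---|---|---|---|
| Day 14 | 14/14 = 100% | 12/14 = 85.7% | 14/56 = 25.0% |
| Day 28 | 28/28 = 100% | 26/28 = 92.9% | 28/56 = 50.0% |
| Day 42 | 42/42 = 100% | 40/42 = 95.2% | 42/56 = 75.0% |
| Day 44 | 44/44 = 100% | 42/44 = 95.5% | 44/56 = 78.6% |
| Day 45 | 45/45 = 100% | 43/45 = 95.6% | 45/56 = 80.4% |

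**Where the definitions part.** 0.8 × 56 = 44.8, so the protocol needs 45 applications. With no missed dose, a stop on or before Day 44 fails the protocol and passes the SAP. With 51 planned applications, 0.8 × 51 = 40.8, so 41 are needed and the last failing stop is Day 40. With 61, 0.8 × 61 = 48.8, so 49 are needed and the last failing stop is Day 48.

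**Consecutive doses.** If days after the stop count as missed, a stop on or before Day 52 leaves at least 56 − 52 = 4 doses missed in a row and breaks the protocol's limit. Under SAP 6.1.7 those days are not expected doses.

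**Interruption branch.** Take a last dose on Day 28. If the last interruption date is Day 35 and the 7 days are recorded as missed, the SAP ratio is 28/35 = 80.0%, a pass. If it is Day 36, the ratio is 28/36 = 77.8%, a fail. The SAP does not say whether a permanent stop is entered as an interruption or whether later days are entered as missed.

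**Reaching the PP set.** Protocol 4.8.6 (stopping the product) is separate from 4.8.7 (leaving the study). Under 4.8.5, subjects whose assignment is disclosed to the investigator stop treatment but are followed to study completion. SAP Table 1 adds: "Subjects that terminate early should return to the study site for the Week 8 assessments". The Week 8 analysis window in SAP Table 2 opens at Day 43 with no upper limit. A Week 8 S-IGA and B-IGA can therefore exist after an early stop, provided the assessment falls on Day 43 or later.

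**The band above 100%.** Missed doses cannot be negative, so (expected − missed) / expected never exceeds 1. That row of SAP 7.4 must be empty.

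**The case against.** The strongest reply is that the SAP percentage is a legitimate on-treatment measure and nothing is hidden. SAP 7.4 also reports expected applications, applications made, days on product and weight used, and SAP 7.1 gives reasons for discontinuation. Protocol 6.1.6 divides by the number of applications expected for each subject, which can be read as subject-specific, and protocol 6.1 leaves detail to the SAP. The protocol defines no PP set, so leaving the consecutive-dose limit out of the PP rule contradicts nothing there. This supports keeping the on-treatment figure. It does not remove the conflict with 4.8.3, which names the period.

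Three stronger readings are tempting, and the documents do not support them.

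- A reader might infer that early stopping can never lower the SAP score. The interruption branch shows that it can. A very early stop with a few misses also fails: 5 of 7 is 71.4%.
- A reader might infer that 80% compliance plus the Week 8 assessments secures PP entry. There is a third condition, the blinded deviation review, and a stop at Day 14 is an obvious candidate for removal. No rule requires the removal, however.
- A reader might infer that all early stoppers reach the PP analysis. SAP 6.1.7 and 8.1 exclude discontinuations for adverse event or lack of efficacy from observed-case analyses from the visit of the last dose day, and the PP analysis uses observed data. Stops for other reasons are outside that exclusion. Its scope is also unclear for subjects who stop the product but stay in the study: 6.1.7 speaks of leaving the study early, 6.1.4.2 of discontinuing treatment, and 8.1 simply of discontinuing.

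**Conclusion.** The mismatch is real and undeclared. Given good adherence before the stop and no later interruption date with recorded misses, a subject who stops on or before about Day 44 passes the SAP's 80% and fails the protocol's. This assumes 56 planned applications; the limit is Day 40 to Day 48 for 51 to 61. The SAP can admit such a subject to the PP set when the Week 8 assessments exist and blinded review raises no important deviation, mainly for stops unrelated to adverse event or lack of efficacy.

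The reach is limited to the compliance table and one supplemental analysis of the co-primary endpoints. The primary ITT analysis is unaffected. The number of subjects cannot be derived: any percentage would need an assumed stop rate and stop timing, and would describe the compliance table, not the PP set. The point is worth correcting because the PP result would otherwise rest on a definition that differs from the protocol's.

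**What to change.** - For the 80% classification and PP entry, divide applications by the planned applications from first dose to the day before the scheduled Week 8 visit, or to Day 56 if there is none. An early-termination visit must not shorten this period.
- Count applications only within the period. Protocol Appendix 10 allows up to 14 days of dosing past Week 8, and without this limit 70 applications over 56 planned would give 125%. State which end date applies if the Week 8 visit is delayed past its window.
- Add the limit of no more than 3 consecutive missed doses to the PP rule, as SAP 7.4 already has it.
- Keep the on-treatment percentage as a second line in the compliance table.
- Remove the band above 100% (minor clean-up).
- SAP V3.0 was written after database lock and unblinding. Report the PP analysis on the protocol-consistent definition beside the existing one, without replacing it, and document the change in the clinical study report.

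The cost is one changed derivation, a few lines of text and one extra PP analysis. Reported compliance and the PP set would be expected to shrink slightly.

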4.8.6. Removal of Subjects from Investigational Product

A subject may discontinue from receiving the IP for any of the following reasons:

- Occurrence of any medical condition or circumstance that, in the opinion of the Investigator, exposes the subject to substantial risk and/or does not allow the subject to adhere to the requirements for IP administration as per the Protocol.
- Occurrence of or considerable worsening of an AE (described in [Section 5.7](#)) that, in the opinion of the Investigator in consultation with the Medical Monitor and Sponsor, represents an unacceptable risk to the subject if he/she continues in the study. The Investigator must follow the subject until the AE resolves or satisfactorily stabilizes.

- IP application must be discontinued immediately in the event of a female subject's pregnancy.
- Subject's decision to withdraw from receiving IP.
- Weight loss of >5% from Baseline, if not dieting or intentionally trying to lose weight, at the Investigator's discretion and after consultation with the Medical Monitor and Sponsor.
- C-SSRS indicative of suicidal ideation
- PHQ-8/PHQ-A score ≥ 15 if determined by Investigator in consultation with a mental health professional.
- Requirement for use of prohibited concomitant medication ([Table 1](#)) after consultation with the Sponsor and Medical Monitor.
- Subjects repeated failure to comply with protocol requirements or study related procedures.

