3.3. Study Population

Study population consists of male and female adolescents (12-17 years old) and adults (≥ 18 years old). Subjects should have a minimum S-IGA of at least “Moderate” (3) and B-IGA

of at least “Mild” (2) at baseline.

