9. SAFETY AND TOLERABILITY ANALYSIS

Safety will be evaluated from reported AEs, physical examinations, local tolerance assessments, changes in clinical laboratory values, changes in vital signs/weight, C-SSRS, PHQ-8, and modified PHQ-A results. No inferential statistical tests will be performed.

All safety analyses will be performed on the Safety population.

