9.4. Vital Signs

Descriptive summaries of observed values, changes from baseline, and percent changes from baseline will be calculated for systolic blood pressure, diastolic blood pressure, heart rate, height, weight, BMI, and oral body temperature by treatment group and visit.

The number of subjects who gain or lose $\geq 5\%$ of their baseline body weight during the course of the study, as well as subjects who gain or lose $\geq 10\%$ of their baseline body weight over the course of the study, will be summarized by treatment group. This summary will be repeated by intentionality of weight loss (intentional or unintentional, as captured on the eCRF).

Shift tables for subjects who shift from their baseline BMI category as defined in [Section 6.1.7](#) (underweight, normal, overweight, obese) to a different BMI category throughout the course of the study will be provided by treatment group and visit. This summary will be repeated by intentionality of weight loss (intentional or unintentional, as captured on the eCRF).

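### One set of fixed BMI categories is applied to subjects aged 12-17 as well as adults, so the BMI shift tables can mislabel adolescents and cannot show a downward shift from the lowest category (minor)

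*SAP*

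**What the plan says.** SAP 6.1.7 computes BMI from weight and height and sorts it into four categories: "Underweight: BMI < 18.5", then 18.5 to 24.9, 25.0 to 29.9, and 30.0 or more. No age or sex condition is attached. On height, the same section says: "For Week 8, Week 8 height will be used to derive BMI since height is not collected at all visits".

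SAP 9.4 plans "Shift tables for subjects who shift from their baseline BMI category as defined in" Section 6.1.7, by treatment group and visit (Table 14.3.4.4). It then adds: "This summary will be repeated by intentionality of weight loss (intentional or unintentional, as captured on the eCRF" (Table 14.3.4.5). The tables are therefore part of the weight-loss reporting.

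Both tables cover all ages. SAP 3.3: "Study population consists of male and female adolescents (12-17 years old) and adults". SAP 9: "All safety analyses will be performed on the Safety population". No weight or BMI table in SAP 14.1 is split by age.

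Weight loss is a monitored risk. Protocol 4.8.6 lists among the reasons for stopping investigational product: "Weight loss of >5% from Baseline, if not dieting or intentionally trying to lose weight". Protocol 5.1.5 asks for an unintentional 5% loss to be reported to the medical monitor.

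**The concern.** BMI changes with age and sex during growth, so a single cut-off does not mean the same thing at 12 as at 40. The SAP does not say where its cut-offs come from. That they are the usual adult ones is general knowledge, not something the documents state. A 12- or 13-year-old of ordinary build can fall below 18.5 and be labelled Underweight at baseline.

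The second effect is a floor. A subject who starts in the lowest category has nowhere lower to go, so the shift table shows no change whatever weight is lost. At stake is how two descriptive tables read for the youngest subjects, on a safety question that the trial follows deliberately.

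The plan is age-specific elsewhere. It uses the CDLQI in place of the DLQI and the modified PHQ-A in place of the PHQ-8 for younger subjects, and SAP 6.1.7 defines a 12-17 age category directly after the BMI list.

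**Working it through.** The documents give no figure for this point, so there is nothing of the plan's to reproduce. The inputs from SAP 6.1.7 are the cut-offs 18.5, 25 and 30. The input from SAP 3.2 is about 420 subjects in total.

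**1. The floor.** With height constant, BMI after a proportional loss L is BMI × (1 − L).
- Start at 18.0: 18.0 × 0.95 = 17.1 and 18.0 × 0.90 = 16.2. Both stay Underweight.
- BMI 18.5 corresponds to 18.5 × 1.50² = 41.6 kg at 150 cm, and 18.5 × 1.60² = 47.4 kg at 160 cm.

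The floor applies to any subject below 18.5, adults included. What is specific to adolescents is that the label itself can be wrong.

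**2. How sensitive the shift table is for everyone else.** A loss L moves a subject down a category only if baseline BMI lies between a cut-off c and c / (1 − L).

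| Cut-off | 5% loss: baseline BMI window | 10% loss: baseline BMI window |
|---|---|---|
| 18.5 | 18.5 to 19.5 | 18.5 to 20.6 |
| 25 | 25 to 26.3 | 25 to 27.8 |
| 30 | 30 to 31.6 | 30 to 33.3 |

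A subject at BMI 22 goes to 20.9 or 19.8 and stays Normal. The table is coarse at any age.

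**3. How many adolescents could be affected (assumptions only).** Suppose adolescents are 2% to 20% of 420, which is 8.4 to 84 subjects, and 10% to 50% of them start below 18.5.
- Low end: 420 × 0.02 × 0.10 = 0.8, about 1 subject (0.2% of the trial).
- High end: 420 × 0.20 × 0.50 = 42 subjects (10%).

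A lognormal BMI shows how strongly the fraction depends on the assumed median m: P(BMI < 18.5) = Φ(ln(18.5/m)/σ), with σ² = ln(1 + CV²). For CV of 14% to 18%, the result is 42% to 73% at medians of 17 to 19, and 18% to 33% at medians of 20 to 21. None of these medians or CVs comes from the documents.

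**4. Two side issues in the same tables.**
- *Gaps.* Unrounded values between 24.9 and 25.0, or between 29.9 and 30.0, have no category. With an assumed lognormal adult BMI of mean 28 or 31 and CV 22%, that is 1.1% to 1.2% of subjects (about 5 of 420). If BMI is classified at one decimal, it is zero.
- *Height at Week 8.* I simulated 2 million adults under the same BMI assumption, with height of mean 170 cm and SD 10 cm and independent measurement errors of SD 0.5 to 1.0 cm at Screening and Week 8. With no weight change at all, 2.1% to 5.0% change category; with one height per adult, none do. I then gave one arm a 2% loss. At mean BMI 28, the between-arm difference in downward shifts falls from 7.6 to between 5.4 and 6.4 percentage points. The net difference (down minus up) stays at 7.6. At mean 31 the net difference likewise stays at 6.6.

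**The case against.** The strongest reply is that these tables are not where the trial looks for weight loss. SAP 9.4 counts subjects who lose at least 5% and at least 10% of their own baseline weight, and repeats the count by intentionality (Tables 14.3.4.2 and 14.3.4.3). It also summarises change and percent change in weight and BMI by visit. Protocol 6.2.3 reports the incidence of loss above 5%, explained or not. The medical-monitor report and the Protocol 4.8.6 criterion run on percent weight. None of these uses a BMI category or leaves adolescents out. Safety is descriptive, with no inferential tests, and nothing in the plan is decided from the two shift tables.

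All of that stands. A reader might infer that harmful weight loss in adolescents would go unseen in this trial. The documents do not support that, because only a category shift is hidden. A reader might also infer that many adolescents would start as Underweight. The documents give neither their number nor their BMI, so any such figure is an assumption.

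The reply does not remove the mislabelling. The percent-weight tables do not correct a category table that assigns adolescents to the wrong group, and they are not split by age either.

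On the side issues, the gap is a missing rounding convention. Using Week 8 height is a defensible single rule where some subjects may still be growing. The height noise rests on an assumed error and moves subjects in both directions, so it does not bias the net difference between arms.

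**Conclusion.** The point holds as a minor one. Followed as written, SAP 6.1.7 and 9.4 classify subjects aged 12-17 by cut-offs that take no account of age or sex, and no subject who starts below 18.5 can show a downward shift in Tables 14.3.4.4 and 14.3.4.5. Both statements follow from the text, apart from the general premise that BMI norms change with age during growth.

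The size cannot be derived. The range of about 1 to 42 adolescents starting below 18.5 reflects only the assumed shares above. Nothing in efficacy, power, type I error or the stopping criteria depends on BMI category, and weight loss in adolescents is still reported directly. The category gaps and the Week 8 height rule are matters of tidying and add no weight to the main point.

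**What to change.** In SAP 6.1.7 and 9.4, limit the four BMI categories and their shift tables to subjects aged 18 or over. For ages 12-17, report BMI-for-age-and-sex z-score or percentile category, with change and shift from baseline, and name the growth reference used. Age, sex, weight and height are already collected, so the cost is SAP wording, a little programming and one extra table that may be small. SAP V3.0 already post-dates database lock and unblinding, so a change made after it should be labelled as post-unblinding.

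Optional tidying: write the cut-offs without gaps (18.5 ≤ BMI < 25, 25 ≤ BMI < 30), and consider one height per adult at all visits to remove measurement noise at Week 8, keeping the re-measured height for adolescents. None of this touches any clinical threshold.
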